7.3.3. Duration of Response

For objective responders, DOR is the time from the first overall response contributing to an objective response as assessed by an independent centralized radiological review committee per RECIST v1.1, to the earlier of death or first overall response of PD occurring after the first overall response contributing to the objective response. Censoring of DOR will follow the same algorithm as the censoring of PFS (see Section [7.3.2](#)).

The total number of responders, the number of subjects who progressed or died, and the number of subjects censored will be summarized. The Kaplan-Meier estimate of median DOR will be presented with its 95% CI. The 95% CI for DOR will be calculated using the Brookmeyer and Crowley's method ([Brookmeyer and Crowley 1982](#)). The DOR analysis will be conducted for Cohorts A, B, and C, respectively.

Subgroup analysis of DOR for Cohort A will be conducted for renal impairment grade and for hepatic impairment grade if there are sufficient responders in each subgroup.

7.3.4. Disease Control Rate

Disease control rate is defined as the proportion of subjects with best response of CR, PR, or SD based on review of scans by an independent centralized radiological review committee per RECIST v1.1. Confirmation of CR and PR is required and documented in the Independent Central Review Charter. This analysis will be based on efficacy evaluable population for subjects in Cohorts A, B, and C, respectively. Subjects who do not have sufficient baseline or on-study response assessment information to be adequately assessed for response status will be included in the denominators in the calculation of DCR. The 95% CI for DCR will be calculated using exact method for binomial distribution.

7.3.5. Overall Survival

Overall survival is defined as the length of time from the start of the study drug (Day 1) until the date of death due to any cause. Date of death will be determined using the Death Report and the Survival Follow-Up eCRFs. Subjects who are lost to follow-up or still alive at the time of analysis will be right-censored at the earlier of the date the subject was last known alive and the clinical data cut-off date for the analysis. The last known alive date is defined as the later of the last study visit and the date the subject was last known alive from the Survival Follow-Up and Subject Status eCRFs.

The number of subjects who died and the number of subjects censored will be summarized. The Kaplan-Meier estimate of median OS will be presented with its 95% CI. The 95% CI for OS will be calculated using the Brookmeyer and Crowley's method ([Brookmeyer and Crowley 1982](#)). The OS analysis will be conducted for Cohorts A, B, and C, respectively.

7.4. Analysis of Other Efficacy Parameters

7.4.1. Largest Percentage Reduction in Sum of Diameters of Target Lesions

For subjects with measurable lesions at baseline, target lesion sizes will be measured by sum of diameters. The best percent change from baseline, defined as the largest decrease in target lesion size during the study, will also be summarized, and a waterfall plot of best percent change will be generated.

Target lesions considered "too small to measure" will be assigned a default value of 5 mm for purposes of this analysis. Likewise, target lesions identified as "not present" at postbaseline assessments will be assigned 0 mm for this analysis. In the event that a target lesion is

unaccounted for in a particular postbaseline timepoint (ie, the assessment is missing or NE), then the overall sum of diameters for target lesions will not be evaluable for that postbaseline timepoint.

7.4.2. Investigator Assessed Efficacy Parameters

Objective response rate, PFS, DOR, and DCR based on review of scans by investigator per RECIST v1.1 will be analyzed in a similar fashion as those parameters assessed by an independent centralized radiological review committee. Confirmation of CR and PR is not required.

Objective response rate, DOR, and DCR assessed by an independent centralized radiological review committee per RECIST v1.1 without requirement of CR and PR confirmation will also be analyzed.

[figure not shown]
7.4.3. Time to Response

[figure not shown]
Time-to-onset of response is defined as the time from the start of the study drug (Day 1) until the date of first confirmed CR or PR as assessed by the independent centralized radiological review committee per RECIST v1.1. The date of first confirmed CR or PR is the date when the criteria for CR or PR is first met and the CR or PR is confirmed at a subsequent timepoint.

[figure not shown]
For responders, time-to-onset of response will be summarized.

7.4.4. Eastern Cooperative Oncology Group Performance Status

Eastern Cooperative Oncology Group performance status at scheduled assessment times will be summarized.

7.6. Pharmacokinetic Analyses

The data will be analyzed by standard population PK methods using appropriate software (eg, NONMEM®). An attempt will be made to evaluate the effect of demographic characteristics and baseline characteristics (eg, age, weight, sex, race, renal function, FGF/FGFR alteration status) on the population PK profile. Additionally, exposure-response analyses for key efficacy and safety parameters may also be considered if there are sufficient data available.

8. SAFETY AND TOLERABILITY

[Appendix A](#) provides a list of planned tables, figures, and listings.

8.1. General Considerations

The analyses for this section will be provided for the safety population. Summary tables may be replaced with listings when appropriate. For instance, an AE frequency table may be replaced with a listing if it only contains a few unique preferred terms reported on relatively few subjects.

8.2. Adverse Events

8.2.1. Adverse Event Definitions

A TEAE is any AE either reported for the first time or worsening of a pre-existing event after first dose of study drug and within 30 days of last dose of study drug. Analysis of AEs (as discussed below) will be limited to TEAEs, but data listings will include all AEs regardless of their timing to study drug administration.

Adverse events will be tabulated by MedDRA preferred term and system organ class. Severity of AEs will be described and graded using the NCI CTCAE v4.03. The CTCAE v4.03 reporting guidelines and grading details are available on the Cancer Therapy Evaluation Program website.

A grading (severity) scale is provided for each AE term. If the toxicity is not included in the CTCAE v4.03 criteria, it will be rated on a scale of 1 to 4 as follows: 1 = mild, 2 = moderate, 3 = severe, and 4 = life-threatening. All toxicities will be graded based on the worst level reached, not the level they may have reached if they had not been treated. When the intensity of an AE changes over time for a reporting period (eg, between visits), each change in intensity will be reported as an AE until the event resolves.

The subset of AEs considered by the investigator to be related to study drug will be considered to be treatment-related AEs. The incidence of AEs and treatment-related AEs will be tabulated. Serious adverse events will also be tabulated.

Any missing onset date, causality, or severity must be queried for resolution. Unsolved missing values will be handled according to the following rules:

- An unsolved missing causality will be considered treatment-related.
- An unsolved missing severity will be identified as an unknown severity.

For purposes of analysis, all AEs will be considered TEAEs unless they can unequivocally be defined as not treatment-emergent.

8.2.2. Clinically Notable Adverse Events

Specific groupings of clinically notable AEs will be considered and the number of subjects with at least 1 event within each grouping will be reported. Such groups consist of AEs for which there is a specific clinical interest in connection with the study drug or AEs that are similar in nature (although not identical). The groups are defined as per [Table 4](#). All clinically notable AEs are defined through reviewing preferred term according to the current MedDRA v21.1.

Table 4: Clinically Notable Adverse Events Groupings

Categories	Preferred Terms
Serous retinal detachment	Serous retinal detachment, detachment of macular retinal pigment epithelium, detachment of retinal pigment epithelium, retinal detachment, subretinal fluid, retinal oedema, chorioretinopathy, retinal pigment epitheliopathy, chorioretinal disorder, retinopathy
Nail toxicity	Nail toxicity, nail bed tenderness, nail bed disorder, nail bed bleeding, nail disorder, nail discolouration, nail discomfort, nail dystrophy, nail hypertrophy, nail ridging, nail infection, onychalgia, onychoclasia, onycholysis, onychomadesis, onychomycosis, paronychia, fungal paronychia
Hyperphosphatemia	Hyperphosphataemia, blood phosphorus increased
Hypophosphatemia	Hypophosphataemia, blood phosphorus decreased

8.2.3. Time-to-First-Event Analyses

For clinically notable AEs identified in [Table 4](#), time-to-first event analyses will be performed.

Time-to-first occurrence of an AE is defined as the time from start of study drug to the date of first occurrence of an AE, that is, time in days is calculated as (start date of first occurrence of AE) – (date of first dose of study drug) + 1. A subject will be censored for time-to-onset if:

- The subject dies with no event.
- The subject receives a new anticancer therapy with no event or before the event has occurred.
- The subject discontinues from the study treatment with no event (up to 30 days after study treatment discontinuation).
- The subject is still ongoing at the cutoff with no event.

In the absence of an event, the censoring date applied will be the earliest from the following dates: date of last dose + 30 days, analysis cutoff, new anticancer therapy start, and death.

The analyses will comprise the following:

- Time-to-onset of first new TEAE (any grade)
- Time-to-onset of first new TEAE of Grade 3 or higher

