- Summary of clinically notable TEAEs leading to dose interruption by category and preferred term
- Summary of clinically notable TEAEs leading to discontinuation of study drug by category and preferred term
- Summary of clinically notable TEAEs by category and preferred term: life-table method
- Summary of Grade 3 or higher clinically notable TEAEs by category and preferred term: life-table method

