3.3.8	Shift Summary of Coagulation Values in CTC Grade – To the Worst Abnormal Value	Safety
3.3.9	Summary of Treatment-Emergent Worsening of Laboratory Abnormalities – Coagulation	Safety
3.3.10	Summary of Laboratory Values – Urinalysis	Safety
Vital Signs		
3.4.1	Summary of Systolic Blood Pressure	Safety
3.4.2	Summary of Diastolic Blood Pressure	Safety
3.4.3	Summary of Pulse	Safety
3.4.4	Summary of Body Temperature	Safety
3.4.5	Summary of Respiratory Rate	Safety
3.4.6	Summary of Body Weight	Safety
ECG		
3.5.1	Summary of PR Interval (ms) From 12-Lead ECG	Safety
3.5.2	Summary of QRS Interval (ms) From 12-Lead ECG	Safety
3.5.3	Summary of QT Interval (ms) From 12-Lead ECG	Safety
3.5.4	Summary of QTcF Interval (ms) From 12-Lead ECG	Safety
3.5.5	Summary of Heart Rate (bpm) From 12-Lead ECG	Safety
3.5.6	Summary of Outliers of QT and QTcF Interval Values From 12-Lead ECG	Safety
3.5.7	Summary of Clinically Significant ECG Abnormalities	Safety

Figures

Figure No.	Title
4.1	Forest Plot of Objective Response Rate (Efficacy)
4.2.1	Kaplan-Meier Estimates of Progression-Free Survival (Efficacy)
4.2.2	Kaplan-Meier Estimates of Duration of Response (Efficacy)
4.2.3	Kaplan-Meier Estimates of Overall Survival (Efficacy)
4.3.1	Waterfall Plot of Best Percent Change of Target Lesion Size From Baseline (Efficacy)
4.3.2	Swimmer Plot of Duration of Treatment (Efficacy)
4.3.3	Forest Plot of Progression-Free Survival (Efficacy)
4.3.4	Forest Plot of Duration of Response (Efficacy)
4.5	Kaplan-Meier Estimates of Time to Adverse Event (Safety)
4.6	Line Graph of Mean Change From Baseline for Selected Laboratory Values (Safety)

Listings

Listing No.	Title
2.1.1	Analysis Population
2.1.2	Subject Enrollment and Disposition Status
2.1.3	Subject Inclusion and Exclusion Criteria Violations
2.2.1	Protocol Deviations
2.4.1	Demographic and Baseline Characteristics
2.4.2	Oncology Disease History
2.4.3	Prior Systemic Therapy
2.4.4	Prior Surgery or Surgical Procedure
2.4.5	Prior Radiation Treatment
2.4.6	Post Therapy
2.4.7	Medical History
2.4.8	Hepatitis History
2.4.9	Prior and Concomitant Medication
2.4.10	FGF/FGFR Alterations
2.5	Study Drug Compliance
2.6.1	Best Overall Response, Duration of Response, Progression-Free Survival, and Overall Survival
2.6.2	Investigator-Reported Assessment by RECIST v1.1
2.6.3	Response Assessment: Target Lesions
2.6.4	Response Assessment: Non-target Lesions
2.6.5	Response Assessment: New Lesions

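### Life-table and Kaplan-Meier displays of time to first clinically notable AE censor death and other exits, so they show a hypothetical on-treatment risk at or above the actual cumulative incidence

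*SAP*

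**What the plan says.** SAP 8.2.3 plans time-to-first-event analyses for the four groupings in SAP Table 4: serous retinal detachment, nail toxicity, hyperphosphatemia and hypophosphatemia. A subject is censored if "The subject dies with no event", and likewise if "The subject receives a new anticancer therapy with no event or before the event has occurred". Discontinuing study treatment without an event also leads to censoring. An event-free subject's censoring date is the earliest of "date of last dose + 30 days, analysis cutoff, new anticancer therapy start, and death".

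The displays follow in SAP 8.2.4 and Appendix A. One is the "Summary of clinically notable TEAEs by category and preferred term: life-table method", with a companion for Grade 3 or higher (Tables 3.2.25 and 3.2.26). Figure 4.5 gives Kaplan-Meier estimates of time to AE.

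Two other provisions matter:
- SAP 8.2.1 counts an AE as treatment-emergent (a TEAE) only up to 30 days after the last dose.
- SAP 8.2.2 reports the crude number of subjects with at least one event per grouping. Tables 3.2.19 and 3.2.20 summarise these events for any grade and for Grade 3 or higher.

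The SAP does not state which risk the curves estimate, and it sets no landmark times for them.

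**The concern.** A subject who dies cannot have the AE later. A subject whose 30-day window has closed cannot have it either, as the SAP defines the event. Kaplan-Meier and life-table methods treat both as still at risk but unobserved, and in effect give them the later experience of those who stay on treatment. The result is the risk that would apply if no one left.

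Such exits will be common. Progression requires withdrawal from treatment (Protocol 5.5.1), participation is expected to average about 6 months (Protocol 4.4), and eligibility asks only for a life expectancy of at least 12 weeks (Protocol 3.1). If the cumulative figure is read as the proportion of treated patients who develop a toxicity, that proportion is overstated. The report would also carry two quite different figures for one grouping, the curve and the crude share, with nothing to explain the gap.

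**Working it through.** **No planned figure to reproduce.** The documents give no AE onset rate, on-treatment death rate or cumulative risk for this analysis. All rates below are assumptions, shown as ranges. The 12-month horizon is also chosen for illustration.

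**Direction.** Kaplan-Meier multiplies each AE hazard by the probability of being free of the AE alone. Aalen-Johansen multiplies it by the probability of being free of both the AE and the competing exit, which is never larger. So 1 − KM is at or above the cumulative incidence whatever the rates.

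**Formulas**, with constant hazards *a* (AE) and *c* (competing exit) and time *t*:
- 1 − KM = 1 − exp(−a·t)
- cumulative incidence = a/(a+c) × [1 − exp(−(a+c)·t)]

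**Inputs**
- AE: 1 − KM at 12 months of 10%, 40% or 60%, so a = −ln(1−F)/12.
- Death without the AE: net 12-month probability D of 3%, 5%, 10% or 20%, so c = −ln(1−D)/12.
- All exits that close the window: mean treatment of 4, 6 or 9 months plus 1 month for the 30-day window, so c = 1/5, 1/7 or 1/10 per month. The central value uses the 6 months in Protocol 4.4 as a proxy; that figure is study participation, not time on treatment.

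**Worked example, F = 40%.** a = −ln(0.6)/12 = 0.0426.
- Death alone, D = 10%: c = 0.0088. Cumulative incidence = 0.829 × (1 − 0.6 × 0.9) = 0.829 × 0.46 = 38.1%.
- All exits, mean 6 + 1 months: c = 0.1429. Cumulative incidence = 0.2296 × (1 − 0.1081) = 20.5%.

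**Cumulative incidence at 12 months (%)**

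| 1 − KM | Death 3% | Death 5% | Death 10% | Death 20% | All exits 4+1 mo | All exits 6+1 mo | All exits 9+1 mo |
|---|---|---|---|---|---|---|---|
| 10 | 9.85 | 9.75 | 9.50 | 8.98 | 3.86 | 4.85 | 5.88 |
| 40 | 39.5 | 39.1 | 38.1 | 36.2 | 16.6 | 20.5 | 24.5 |
| 60 | 59.2 | 58.7 | 57.4 | 54.7 | 26.6 | 32.3 | 38.1 |

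The death-only gap runs from 10 − 9.85 = 0.15 to 60 − 54.7 = 5.3 points. The all-exit gap runs from 10 − 5.88 = 4.1 to 60 − 26.6 = 33.4 points.

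**Very early event** (assumed: 95% of onsets by month 1). The death-only gap at 12 months is at most 0.6 points for D of 5% to 20%. The all-exit gap is about 3 to 6 points. That second figure is on the high side, because the model allows exits in the first month, whereas last dose plus 30 days cannot fall that early.

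**Check by simulation** (N = 140, 2,000 runs, 12 months, true 1 − KM of 40%, 10% net death risk, mean 6 months on treatment plus 1, cut-off 6 to 30 months after entry):

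| Estimate | Mean |
|---|---|
| Kaplan-Meier | 39.6% |
| Monthly life table | 39.4% |
| Aalen-Johansen, death competing | 37.7% |
| Aalen-Johansen, all exits competing | 21.0% |
| Crude share with an event (all follow-up) | 21.5% |

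The life table behaves like Kaplan-Meier. Death accounts for little of the gap; the other exits account for most of it.

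**The case against.** The best defence is that the SAP never presents these curves as the share of treated subjects. Section 8.2.3 concerns time to onset. Censoring at the end of exposure targets the risk while on drug, which is a legitimate safety question, and the crude tables answer the other one. In the simulation the crude share is within half a point of the all-exit Aalen-Johansen estimate. This stands: the share is not lost, and treating discontinuation as a competing event is a choice of estimand. What remains is that the SAP does not say that the curve is an on-treatment risk, or that this reading needs exits to be independent of AE risk. The crude count also gives no time course and makes no allowance for subjects still on treatment at the cut-off.

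Three stronger readings are tempting and not supported:
- *Kaplan-Meier risks will differ between cohorts merely because progression rates differ.* With independent exits, 1 − exp(−a·t) does not contain *c*, so 1 − KM is the same in each cohort when the AE hazard is the same. It is the cumulative incidence, and hence the gap, that changes with *c*.
- *Tabulated 6- or 12-month risks are wrong.* The SAP specifies no such timepoints.
- *Death drives a large bias.* Death alone accounts for a few points; a roughly twofold gap appears only when every window-closing exit is counted. Nor do the documents give onset times that would establish any Table 4 grouping as late-onset.

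**Conclusion.** The point holds as a low-cost improvement to a secondary safety display. The planned estimates are hypothetical on-treatment risks, and they lie at or above the actual cumulative incidence among treated subjects; that direction needs no assumed rate. The size does. Under constant, independent hazards and the ranges above, the 12-month excess is about 0.2 to 5 points for death alone and about 4 to 33 points for all exits that close the TEAE window. If hyperphosphatemia appears very early, as assumed in the early-onset case, death hardly affects its estimate. Nothing here touches the primary endpoint or a decision rule, and the SAP does not contradict itself.

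**What to change.** In SAP 8.2.3, Tables 3.2.25 and 3.2.26 and Figure 4.5:

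1. Present the Aalen-Johansen cumulative incidence, with death before the AE and within the TEAE window as a competing event. This curve still censors the other exits, so it should not be labelled as the share of treated subjects.
2. Add a supplementary curve in which every exit that closes the window competes. Date the exit at the earliest of last dose plus 30 days, new anticancer therapy and death, so that AEs in the 30 days after the last dose still count. Censor only at the analysis cut-off. This curve corresponds to the share of treated subjects over time.
3. Keep the present Kaplan-Meier and life-table estimates, labelled as risk conditional on remaining on treatment.

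The cost is SAP wording and some programming on data already collected. The drawbacks are more curves per grouping and a less direct comparison with studies that report Kaplan-Meier alone, which keeping the present estimate largely offsets.

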5.6. Withdrawal of Subjects From Study

If the subject discontinues study treatment and actively withdraws consent for collection of follow-up data (safety follow-up or disease assessment), then no additional data collection should occur; however, subjects will have the option of withdrawing consent for study treatment but continuing in the follow-up period of the study for safety/efficacy assessments.

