6.4. Follow-Up

6.4.1. Safety Follow-Up

The safety follow-up period is the interval between the EOT visit and the scheduled follow-up visit, which should occur 30 to 35 days after the EOT visit (or after the last dose of study drug if the EOT visit was not performed). Adverse events and SAEs must be reported up until at least 30 days after the last dose of study drug, the date of the follow-up visit, or until toxicities resolve, return to baseline, or are deemed irreversible, whichever is longer. Reasonable efforts should be made to have the subject return for the follow-up visit and report any AEs that may occur during this period.

If a subject is scheduled to begin a new anticancer therapy before the end of the 30-day safety follow-up period, then the safety follow-up visit should be performed before new anticancer therapy is started. Once new anticancer therapy has been initiated, the subject will move into the survival follow-up period.

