3.2. Sample Size Considerations

Approximately 100 subjects with documentation of FGFR2 translocation from the central genomics laboratory are planned for the final analysis of the primary endpoint of ORR. With the assumed rate of 33% for the intervention, a sample size of approximately 100 subjects would provide > 95% probability to have a 95% CI with lower limit of > 15%, assuming 10% lost to follow-up. Up to 20 subjects will be enrolled in Cohort B and Cohort C (United States only), respectively, which will provide > 80% chance of observing at least 4 responders in each cohort, if the underlying ORR is 30%.

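### The time-to-first-AE rule has no censoring date for withdrawal of consent or loss to follow-up, so a few unobserved days can count as event-free; the effect on cumulative AE risk is small

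*SAP*

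**What the plan says.** SAP 8.2.3 plans time-to-first-event analyses for the clinically notable AE groups of SAP Table 4: serous retinal detachment, nail toxicity, hyperphosphatemia and hypophosphatemia. It gives four reasons for censoring: death, new anticancer therapy, discontinuation of study treatment (up to 30 days afterwards), and still ongoing at the cutoff. It then fixes the date for a subject without the event as "the earliest from the following dates: date of last dose + 30 days, analysis cutoff, new anticancer therapy start, and death". The only kind of discontinuation named is from treatment, not from the study.

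The window matches the TEAE definition in SAP 8.2.1, which covers events "after first dose of study drug and within 30 days of last dose of study drug".

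Two Protocol passages show that AE observation can stop inside that window. Under Protocol 5.6, if a subject stops treatment and also withdraws consent for follow-up data, "then no additional data collection should occur". Protocol 6.4.1 places the safety visit 30 to 35 days after the end-of-treatment visit, but attendance is best-effort: "Reasonable efforts should be made to have the subject return for the follow-up visit".

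For overall survival, SAP 7.3.5 handles early loss explicitly. Such subjects are "right-censored at the earlier of the date the subject was last known alive and the clinical data cut-off date for the analysis".

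**The concern.** A censoring date should not fall later than the end of observation. Under SAP 8.2.3 as written, a subject who leaves the study event-free the day after the last dose stays in the risk set for about 29 more days, in which no AE could be recorded. This adds to the denominator with no chance of adding an event.

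The outputs at stake are the two life-table tables and Figure 4.5, which describe the AEs that the SAP singles out as of specific clinical interest. SAP 8.2.4 asks for the listed AE summaries by cohort, so in Cohort B or C one such subject is 1/20 of the starting risk set. Understatement is also the unwelcome direction for a safety output.

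**Working it through.** The documents give no figure for this analysis, so there is nothing of the plan's own to reproduce. The check concerns direction and size.

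**Direction.** Compare the rule as written with complete observation of everyone to last dose + 30 days. The rule removes any event that a lost subject would have had in the unobserved days, and keeps that subject at risk instead. At each event time the number of events is equal or lower and the risk set is equal or larger. The estimated cumulative risk can therefore only be equal or lower.

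**Inputs for size.**
- Horizon T = 180 days and mean treatment time m = 150 days (range 90 to 270). These are assumptions, guided by the average participation of about 6 months in Protocol 4.4. Treatment times are taken as exponential.
- Share w unobserved from the last dose: 5% to 20%, an assumption. The documents give no figure.
- True Day 180 risk R: 48.8%, borrowed from the Phase 1 hyperphosphatemia rate in Protocol 1.3.2 as an illustration (it is a crude rate, not a Day 180 risk), plus 10% and 5% as assumptions.
- Constant hazard λ = −ln(1 − R)/T, unchanged after the last dose.

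**Formula.** With k = 1 − exp(−30/m), the unobserved fraction of the risk set is w[1 − exp(−t/m)] up to Day 30 and w·k afterwards. Integrating to T gives an effective loss of L = w[30 − m·k + (T − 30)·k] days. The estimate under the rule is 1 − exp[−λ(T − L)].

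**Worked example** (R = 48.8%, m = 150, w = 10%):
- λ = 0.6694/180 = 0.003719 per day
- k = 1 − exp(−0.2) = 0.1813
- L = 0.10 × [30 − 27.19 + 27.19] = 3.0 days
- Estimate = 1 − exp(−0.003719 × 177) = 48.2%, a shortfall of 0.57 points

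| True risk | w | Mean treatment (days) | As written | Shortfall (points) |
|---|---|---|---|---|
| 48.8% | 10% | 150 | 48.2% | 0.57 |
| 48.8% | 20% | 150 | 47.6% | 1.16 |
| 48.8% | 20% | 90 | 47.0% | 1.82 |
| 10% | 10% | 150 | 9.84% | 0.16 |
| 10% | 20% | 90 | 9.50% | 0.50 |
| 5% | 10% | 150 | 4.92% | 0.08 |
| 5% | 5% | 270 | 4.98% | 0.02 |

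Kaplan-Meier simulation (400 runs of 2000 subjects, m = 150) agrees. As written versus censored at end of observation, it gives 48.2% versus 48.8% at w = 10% and 47.5% versus 48.7% at w = 20% for the common event, and 9.8% versus 10.0% at w = 10% for the 10% event.

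**If the hazard falls after the last dose.** A second simulation used m = 150, w = 10% and the same on-drug hazard as the 48.8% event. Day 180 risk was:

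| Off-drug hazard relative to on-drug | Everyone observed | As written | Censored at end of observation |
|---|---|---|---|
| 50% | 45.8% | 45.5% | 46.1% |
| 25% | 44.2% | 44.1% | 44.6% |
| 0% | 42.5% | 42.5% | 43.0% |

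The understatement shrinks to zero, and the correction then overshoots by 0.3 to 0.5 points.

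**The case against.** The best defence is that the rule fits the planned observation window. TEAEs run to last dose + 30 days, AE reporting is required for at least that long, and Protocol 5.5.1 and 5.6 let subjects stop treatment yet stay in follow-up. For them the 30 days are observed and the rule is right. This stands, and it limits the problem to subjects who withdraw follow-up consent or are lost within those 30 days. It does not repair the rule for that group.

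The second defence is pharmacological. Protocol 1.3.2.1 gives a terminal half-life of 10.9 to 31.4 hours, and Protocol 5.4.3 describes hyperphosphatemia as an on-target effect, so the hazard may well drop off drug. Censoring at last contact gives lost subjects the hazard of a risk set that is mostly still on treatment. This also stands: in the simulation with the off-drug hazard at 25% or less, the existing rule lies nearer to complete observation than the corrected one. The differences are fractions of a point either way.

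A reader might infer something stronger in three ways, none of which the documents support.
- One could take "assuming 10% lost to follow-up" (SAP 3.2) as the plan's forecast of early loss. It was set for the Cohort A response-rate sample size, and says nothing about loss within 30 days of the last dose.
- One could build a larger effect by having every lost subject leave on Day 8. The Day 38 shortfall is then p × [S(8) − S(38)]. With 50% incidence by Day 63, S(8) = 0.916 and S(38) = 0.658, so p = 10% gives 2.6 points; with 80% incidence (0.815 and 0.379) it gives 4.4. The arithmetic is right, but no document supports mass exit on Day 8 or those incidences.
- One could say that the bias is worst for early-onset events. That holds only if loss is early too. Otherwise most subjects who will have the event have had it before stopping, and the rule affects only those still event-free.

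**Conclusion.** The gap is real and minor. SAP 8.2.3 fixes the censoring date by a closed list that omits the end of observation. No other section repairs it, and the OS rule in the same SAP shows how it can be handled. Against complete observation, the direction is certain: equal or lower cumulative risk. The size is about 0.02 to 1.8 points at Day 180, resting on 5% to 20% lost from the last dose, mean treatment of 90 to 270 days, exits spread over treatment, event risks of 5% to 48.8%, and an unchanged hazard off drug. It moves towards zero as the off-drug hazard falls, and is nil if nobody is lost early. Only the time-to-first-event and life-table outputs are touched. Crude AE counts and percentages and the primary endpoint are not.

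**What to change.** In SAP 8.2.3, add to the list of censoring dates: *date of withdrawal of consent for follow-up, or date of last contact or study visit if lost to follow-up*. Apply it to Tables 3.2.25 and 3.2.26 and Figure 4.5.

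The cost is one phrase and one derived date. SAP 7.3.5 already uses the last study visit and the Survival Follow-Up and Subject Status forms, and SAP 6.2 summarizes study discontinuation by reason, so new data collection is probably unnecessary. The forms themselves are not in the documents, and this should be confirmed. A last-known-alive date is not the same as a last AE assessment, so the programming specification should say which contacts count.

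The downside is that censoring at last contact assumes lost subjects share the hazard of those still observed. If the hazard falls off drug, the corrected curves may slightly overstate risk. A footnote giving the number of subjects censored for this reason, by cohort, would let a reader judge whether it matters.
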